This study will assess whether checkpoint agonist(s), initially drives CD8+ T cells intra-tumorally, which helps avelumab (PD-L1 inhibitor) to augment the response in a limited series of indications. Based on emerging preclinical and clinical data, studies to evaluate combinations of avelumab with other immune modulators may follow.

Table 1: Treatment Arms of Avelumab in Combination with Other Cancer Immunotherapies with or without Radiation.

Categories	Treatment Arm	Treatment	Projected Phase I Enrollment
I. Avelumab + Checkpoint Agonist(s)	A	Avelumab + Utomilumab (4-1BB)	*Max. 14
	B	Avelumab + PF-04518600 (OX40)	*Max. 14
	C	Avelumab + Utomilumab (4-1BB) + PF-04518600 (OX40)	**Max. 18
II. Avelumab + Checkpoint Agonist(s) + XRT	D	Avelumab + Utomilumab (4-1BB) + XRT	***Max. 32

*In Arm A, B and C, the MTD will be provided by Pfizer. The projected number of patients to be enrolled in Phase I is for MTD expansion cohorts only. This number does not include patients enrolled on the previous avelumab dosing schedule (prior to Version 05).

** The projected number of patients to be enrolled in Phase I includes dose escalation and MTD expansion cohort.

***In Arm D, the projected number does not include patients enrolled on the previous avelumab and radiation dosing schedule (prior to Version 08 and Version 09). Please refer to Section 9.3 for Sample Size Determination.

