3.1.2 Part II: MTD Expansion

Once the MTD is determined, an additional 14 patients will be enrolled on the MTD expansion cohort for additional characterization of safety and response, and for correlative studies to establish the recommended phase 2 dose (RP2D) for each combination.

For patients enrolled in the MTD expansions of Arms A-C, biopsies, blood samples will be collected at baseline, between Cycle 1 Day 12-15 (prior to study drug dosing), prior to Cycle 3 Day 1 study drug dosing, and at the time of progression (if patient had an initial response of stable disease ≥ 6 months, partial response, or complete remission) to evaluate biological response or predictive markers in blood, tumor, and tumor environment and their relationships to drug exposure, clinical response, or other biologic response markers.

For patients enrolled in the MTD expansion of Arm D, biopsies will be collected at baseline, prior to Cycle 3 Day 1 dosing, and at the time of progression (if patient had an initial response of stable disease ≥ 6 months, partial response, or complete remission). For patients enrolled in the MTD expansion of Arm D, blood samples will be collected at baseline, prior to Cycle 1 Day 1 dosing, prior to Cycle 1 Day 15 dosing, prior to Cycle 2 Day 1 dosing, prior to Cycle 3 Day 1, and at the time of progression (if patient had an initial response of stable disease ≥ 6 months, partial response, or complete remission). We will also evaluate mutation burden and immune scoring. Cell free DNA from patient's blood samples will also be analyzed.

Once the pharmacodynamic, toxicity, and efficacy data is available, the Investigational Cancer Therapeutics team will collaborate with Pfizer and disease-specific experts in each department to a) identify the most effective combination dose for these tumor types, as well as other tumor types of interest, based on toxicity, biology, and target interaction, and b) evaluate the most appropriate methods for determining progression-free survival and other clinical variables that may vary across tumor types.

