7.3 Biopsy Analyses

For patients in the MTD expansion cohorts of Arms A-C, tumor tissue will be obtained pre- treatment (baseline), between Cycle 1 Day 12-15 (prior to study drug dosing), prior to Cycle 3 Day 1 study drug dosing, and at progression (if achieved stable disease \geq 6 months, partial response, or complete remission) provided there is technically biopsiable tumor, and it is safe for patient to undergo biopsy.

For patients in the escalation cohorts of Arm C (patients enrolled prior to Version 05), tumor tissue will be obtained pre- treatment (baseline), prior to Cycle 2 Day 1 dosing, and at progression (if achieved stable disease \geq 6 months, partial response, or complete remission) provided there is technically biopsiable tumor, and it is safe for patient to undergo biopsy.

For patients in the de-escalation and MTD Expansion cohort of Arm D, tumor tissue will be obtained pre- treatment (baseline), prior to Cycle 3 Day 1 dosing, and at progression (if achieved stable disease \geq 6 months, partial response, or complete remission) provided there is technically biopsiable tumor, and it is safe for patient to undergo biopsy.

Correlative studies for biomarker analyses will be performed during this study.

A fresh core needle biopsy (CNB) will be obtained solely with the purpose of research studies (pre-treatment samples) and sent to the Institutional Tissue Bank (ITB) immediately after collection. Up to 5 cores will be obtained from the CNB procedure. The number of cores obtained will be affected by the patient clinical condition at the time of biopsy and determined by the radiologist who is performing the procedure. It is important to note that in some of these trials, the biopsy sample will also be required for clinical diagnosis. In such case, the first specimen will be prioritized for clinical specimen processing. In most instances, a rapid on site evaluation (ROSE) is available locally to evaluate the adequacy of clinical sample, thus additional biopsies may be procured for this research project. Nevertheless, the amount tissue available for correlative studies can be variable. Core biopsy is typically performed using 21-18 gauge needle and with condition permitting, up to 5 cores should be collected.

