For Arms A, B, and C, subjects must have at least two lesions amenable to biopsy and response evaluation. Tumor lesions used for biopsy should not be lesions used as RECIST target lesions. Every effort will be made to biopsy the same lesion at each time point.

For Arm D, subjects should have at least three lesions amenable to biopsy, response evaluation, and radiation. Tumor lesions used for biopsy should not be lesions used as RECIST target lesions. Every effort will be made to biopsy the same lesion at each time point. In addition, the radiated lesion will also be biopsied at each time point. However, if patients in Arm D do not have three separate lesions, patients will be eligible if there are two lesions, in which one is > 2 centimeters (short axis) and can be used for both biopsy and response evaluation.

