9.7 Biomarker Analysis

For the primary objective, we will analyze changes in CD8 expression before and after treatment using a paired t-test if the data are Normally distributed, and a Wilcoxon signed rank test if not. With 14 patients in each cohort, we will have 90% power (assuming 2-sided 5% alpha) to detect a 0.94^*s mean difference where “s” is the standard deviation of the differences. With all 7 cohorts combined, we will have 98 patients, which yields 90% power to detect a 0.33^*s mean difference. We will correlate CD8 expression with clinical benefit (CR/PR/SD>6m) using ROC curve analysis. With 98 patients, we would have 90% power to detect an area under the ROC curve of 0.69 (vs. 0.5 which is the null value) assuming 5% alpha and half the patients showing clinical benefit.

For the exploratory objective, we will conduct similar analyses on additional unspecified biomarkers.

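### The primary CD8-benefit ROC in Section 9.7 pools different regimens without stratifying by arm, so differences between arms can pass for an association

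*Combined protocol and SAP*

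**What the plan says.** Section 2.1.1 makes the relation of pre- and post-treatment CD8 to clinical benefit (CR, PR, or SD beyond 6 months) a primary objective. The analysis is described only in Section 9.7, in two parts.

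- **CD8 change.** A paired test, sized per cohort ("With 14 patients in each cohort, we will have 90% power" for 0.94 SD) and again for the pool ("With all 7 cohorts combined, we will have 98 patients", for 0.33 SD).
- **CD8 against benefit.** "We will correlate CD8 expression with clinical benefit" by ROC analysis. This part is sized for the pool only: 98 patients, AUC 0.69 against 0.5, 90% power, 5% alpha, half with benefit.

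For the ROC, Section 9.7 does not state the biopsy visit, the lesion, the handling of missing biopsies, or any stratification by arm.

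Section 3.1 lists the current arms, all with avelumab: utomilumab (A), PF-04518600 (B), both (C), and utomilumab with radiation (D). On-treatment biopsies differ by arm. The Arms A-C expansions have two, "between Cycle 1 Day 12-15 (prior to study drug dosing), prior to Cycle 3 Day 1 study drug dosing" (Section 3.1.2). In Arm D, "tumor tissue will be obtained pre- treatment (baseline), prior to Cycle 3 Day 1 dosing" (Section 7.3), and Section 7.3 adds: "In addition, the radiated lesion will also be biopsied at each time point". Section 9.2 counts four arms, whereas Section 9.7 still counts seven cohorts.

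**The concern.** A pooled ROC compares every patient with benefit against every patient without, including pairs from different arms. Suppose one regimen raises CD8 and also gives more benefit by another route. Its patients then supply high CD8 values and many of the benefits, and the pooled AUC rises above 0.5 although CD8 says nothing about who benefits on a given regimen. If the high-CD8 regimen gives less benefit, the AUC falls below 0.5, and a real within-arm association can be hidden.

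At stake is the reading of a primary objective. A positive pooled result could be reported as CD8 marking benefit when it reflects only which combination the patient received.

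**Working it through.** **1. The plan's own figures.** All three reproduce.

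- Paired t, two-sided 5%: n = 14 at 0.94 SD gives 90.1% power; n = 98 at 0.33 SD gives 89.9%.
- ROC, Noether formula: N = (z₀.₉₇₅ + z₀.₉₀)² / [12 c(1−c)(AUC − 0.5)²], with c = 0.5. This is (1.960 + 1.282)² / (12 × 0.25 × 0.19²) = 10.507 / 0.1083 = 97.02, or 98 for two equal groups. Power at 98 is 90.3%.

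The arithmetic is sound for one homogeneous group. The formula has no term for arm.

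**2. Pooled AUC with no within-arm association.** Take equal-sized arms, CD8 normal with SD 1 and mean mᵢ in arm i, and benefit rate pᵢ:

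AUC = Σᵢⱼ pᵢ(1−pⱼ) Φ((mᵢ−mⱼ)/√2) / Σᵢⱼ pᵢ(1−pⱼ)

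Example (assumed): four arms, one with CD8 higher by 1 SD and benefit 40%, the other three at 20%.

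- Denominator: (0.4 + 3 × 0.2) × (0.6 + 3 × 0.8) = 1.0 × 3.0 = 3.0.
- Benefit in the high arm against no benefit elsewhere: 0.4 × 2.4 × 0.760 = 0.730.
- Benefit elsewhere against no benefit in the high arm: 0.6 × 0.6 × 0.240 = 0.086.
- Pairs with equal means: (0.4 × 0.6 + 0.6 × 2.4) × 0.5 = 0.840.
- AUC = 1.656 / 3.0 = 0.55.

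With benefit of 10%, 20% or 60% in the high arm, the same formula gives 0.47, 0.50 and 0.59. There is no bias unless both CD8 and benefit differ by arm.

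**3. Rejection rate of the nominal 5% test.** Simulation with four arms of 14 (56 patients) and no within-arm association. Arm means are equally spaced over 1 SD and benefit rates equally spaced from 15% to 50%, unless stated. All these inputs are assumptions.

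| Scenario | Mean pooled AUC | Pooled test rejects |
|---|---|---|
| CD8 and benefit in the same order | 0.56 | about 11% |
| Orders unaligned (CD8 ranks 2, 4, 1, 3) | 0.50 | 5% |
| Averaged over all orderings | – | about 7% |
| Equal benefit rates | 0.50 | 5% |
| Aligned, CD8 spread halved, or benefit 20% to 35% | 0.53 | about 6% |
| Aligned, means spanning 1.5 SD | 0.58 | about 17% |

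Reversing the aligned order mirrors the AUC to 1 − 0.56 = 0.44. The arm-stratified rank test rejects about 5% throughout.

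**4. Cost of stratifying.** If the arms do not differ, with true AUC 0.69, n = 56 and 25% benefit, power falls from about 55% to 51%. Repeated runs put the loss at 3 to 5 points.

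**5. Visit and lesion.** Avelumab starts at Cycle 1 Day 15 in the Arms A-C expansions and in Arm D (footnotes to the two Schedules of Assessments). The Day 12-15 biopsy therefore precedes avelumab and the Cycle 3 Day 1 biopsy follows it. Baseline and Cycle 3 Day 1 are the two fixed visits these cohorts share. Cycle 3 Day 1 falls at about the first restaging (Section 7.2), and biopsy then depends on feasibility and safety (Section 7.3). If patients without benefit are missing at random with respect to CD8, a true AUC of 0.69 stays 0.69. If 20% to 60% of them are missing and low CD8 makes loss more likely (assumed log-odds slope 1 to 2 per SD), the observed AUC runs from 0.65 down to 0.49.

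**The case against.** The inflation depends on alignment. If the CD8 ordering of the arms does not track the benefit ordering, the pooled test holds its 5% level, and under milder spreads it rejects only about 6%. None of the spreads or benefit rates comes from the documents, and Section 9.7 ties no go/no-go decision to the AUC. This stands, and it keeps the point moderate.

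The CD8 change analysis is largely outside the concern. It is sized per cohort as well as pooled, and in a paired test each patient is his or her own control, so differences in CD8 level between arms cannot confound it.

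Three stronger readings are tempting, and the documents do not support them.

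- **That the plan combines biopsies from before and after avelumab.** Section 9.7 names no visit. Baseline and Cycle 3 Day 1 are common to the Arms A-C expansions and Arm D, so an unmixed analysis is available.
- **That the ROC uses only patients still on study at week 8.** The objective covers pre-treatment CD8 too, and a baseline ROC loses nobody at week 8. For Cycle 3 Day 1 values, losing patients without benefit does not by itself bias an AUC; the loss must relate to CD8. Nor can the loss be estimated from the 11.6-week median PFS in Section 1.2.1, which is avelumab alone in NSCLC. First imaging is at week 8, and Section 6.2 allows treatment past progression.
- **That Day 12-15 must be the main contrast.** Section 1.1 says: "This study will assess whether checkpoint agonist(s), initially drives CD8+ T cells intra-tumorally, which helps avelumab (PD-L1 inhibitor) to augment the response". That biopsy bears on the first half of the hypothesis, but the stated primary objective is pre- and post-treatment CD8 against benefit. Promoting it is a preference.

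**Conclusion.** The concern holds for the ROC. As written, Section 9.7 tests a primary objective on a pool of different regimens with nothing to separate a within-arm association from a difference between arms. The bias can go either way and needs both CD8 and benefit rate to vary by arm.

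Its size cannot be derived from the documents. Under the assumptions shown, the true type I error of the nominal 5% test lies between 5% and about 11%, and reaches about 17% with a wider CD8 spread. The visit, the lesion and the missing biopsies are gaps in specification; they are not errors that the plan commits. They should be closed in the same edit, because they decide what the pooled ROC measures.

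**What to change.** In Section 9.7:

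1. Make the main ROC test arm-stratified, by a stratified rank test or by combining within-arm AUCs. Keep the unstratified pooled AUC as a supportive summary.
2. For the pooled analysis, use the visits common to the Arms A-C expansions and Arm D (baseline and Cycle 3 Day 1), and take the non-irradiated lesion in Arm D.
3. Report the ROC for baseline CD8 in all treated patients separately from the ROC for Cycle 3 Day 1 CD8. Label the latter a landmark analysis in patients biopsied at week 8, and give the number excluded.

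This changes analysis wording only and needs no further patients or biopsies. The cost is the 3 to 5 points of power shown above if the arms turn out not to differ. An arm in which no patient, or every patient, benefits adds nothing to the stratified test. At an assumed 15% benefit, an arm of 14 has no benefit with probability 0.85¹⁴, about 10%, so the number of informative arms should be reported.

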9.8 Final Analysis

The final analysis for each study treatment arm will take place after the MTD expansion had been completed. Additional data summarization may take place after all available survival data are collected, or after investigator decision, as appropriate.

10.0 QUALITY CONTROL AND QUALITY ASSURANCE

This study will be monitored by the MD Anderson IND Office and a protocol-specific monitoring plan will be followed.

11.0 DATA HANDLING AND RECORD KEEPING

11.1 Case Report Form/ Electronic Data Record

All patients who meet eligibility criteria and are enrolled in this trial will be registered in Clinical Oncology Research Database (CORe) at the University of Texas MD Anderson Cancer Center at Houston. Data will be collected and stored in the Investigational Cancer Therapeutics database, Molecular and Clinical Data Integrated Platform (MOCLIP).

11.2 Record Retention

The investigator must maintain adequate and accurate records to enable the conduct of the study to be fully documented and the study data to be subsequently verified. These documents should be classified into two separate categories: investigator's study file and subject/ patient data.

The investigator's study file will contain all essential documents such as the protocol/ amendments, case report and query forms, patient information and informed consent form, ethics committee and regulatory authority approval, notification of the federal regulatory authority and competent regional authorities (if applicable), drug records, staff curriculum vitae and authorisation forms, and other appropriate documents/correspondence, etc.

Patient data includes patient hospital/clinic records (e.g. medical reports, surgery reports appointment book, medical records, pathology and laboratory reports, ECG, etc.), signed informed consent forms and patient screening and eligibility screening forms.

The investigator must keep these two categories of documents on file for at least 15 years (or longer, as legally required) after completion or discontinuation of the study. The documents must be archived in a secure place and treated as confidential material.

11.3 Audits and Inspections

This study may be audited by the IND sponsor, any person authorized by the IND sponsor, or the competent health authority in order to determine the authenticity of the recorded data and compliance with the study protocol.

The investigator must be aware that source documents for this trial should be made available to appropriately qualified personnel working on behalf of the authority inspectors after appropriate notification for the purposes of source data verification and proper review of the study progress. The verification of the case report form data must be done via direct inspection of the source documents. The investigator agrees to comply with the IND sponsor and regulatory authority requirements regarding the auditing of the study.

All materials used in clinical studies are subjected to quality control.

12.0 DEFINITION OF END OF TRIAL

End of Trial is defined as the time at which it is deemed that sufficient patients have been recruited and completed the study as stated in the regulatory application (ie, Clinical Study Application (CTA)). Poor recruitment (recruiting less than the anticipated number in the CTA) is not a reason for premature termination but is considered a normal conclusion.

End of Trial is defined as Last Patient Last Visit.

13.0 SPONSOR DISCONTINUATION CRITERIA

Premature termination of this study may occur because of a regulatory authority decision, change in opinion of the IRB/IEC, drug safety problems, or at the discretion of the MDACC IND Office. In addition, Pfizer retains the right to discontinue development of avelumab, utomilumab, PF-04518600 at any time.

If a study is prematurely terminated or discontinued, Pfizer or the MDACC IND Office will promptly notify the investigator. As directed by Pfizer, all study materials must be collected and all CRFs completed to the greatest extent possible.

14.0 APPENDICES

Appendix 1: Adverse Event Categories for Determining Relationship to Test Drug

Appendix 2: ECOG Performance Status

Appendix 1 – Adverse Event Categories for Determining Relationship to Test Drug

(a) Related (must have one of them)

This category applies to those adverse events that are considered to be related to the test drug. An adverse event may be considered related if:

1. It follows a reasonable temporal sequence from administration of the drug
2. It cannot be reasonably explained by the known characteristics of the subject's clinical state, environmental or toxic factors or other modes of therapy administered to the subject
3. It disappears or decreases on cessation or reduction in dose. (There are important exceptions when an adverse event does not disappear upon discontinuation of the drug, yet drug-relatedness clearly exists: e.g. (1) bone marrow depression, (2) tardive dyskinesias.)
4. It follows a known pattern of response to the suspected drug
5. It reappears upon rechallenge

(b) Unrelated

This category is applicable to those adverse events which are judged to be clearly and incontrovertibly due only to extraneous causes (disease, environment, etc.) and do not meet the criteria for drug relationship listed under related.

Appendix 2 – ECOG Performance Status

GRAD	SCALE
0	Fully active, able to carry out all pre-disease performance without restriction
1	Restricted in physically strenuous activity but ambulatory and able to carry out work of a light or sedentary nature, e.g., light housework, office work
2	Ambulatory and capable of all self-care, but unable to carry out work activities. Up and about more than 50% of waking hours.
3	Capable of only limited self-care, confined to bed or chair more than 50% of waking hours
4	Completely disabled. Cannot carry out any self-care. Totally confined to bed or chair.
5	Dead

